### 5.2. Safety Endpoints

Safety endpoints will be analyzed over the entire treatment and follow-up period.

1. Adverse events (AEs) and serious adverse events (SAEs)
2. Vital signs
3. Physical examination of the nasal mucosa
4. Blood chemistries and hematology
5. Electrocardiogram (ECG) results
6. Suicidality: Frequency of subjects with suicidal ideation at any time during the treatment period using the Columbia-Suicide Severity Rating Scale (C-SSRS)
7. Depression: HAM-D17 Scores

## 6. DEFINITION OF ANALYSIS SETS

The study analysis populations will consist of the following:

**Safety Analysis Set:** All subjects who received an implant.

**PK analysis set.** All subjects who provided sufficient data to determine PK parameters will be included in this analysis set.

## **7. HYPOTHESES TO BE TESTED**

There are no statistical hypotheses being tested in this study. All data will be presented as descriptive statistics.

## **8. SAMPLE SIZE CONSIDERATIONS**

The primary endpoint is PK. The sample size of 6 evaluable drug-treated subjects per dose level is standard for PK studies.

## **9. DATA QUALITY ASSURANCE**

Data quality assurance will start with training of clinical investigative staff on data collection and including an Electronic Data management System (EDMS) User Guide. The EDMS User Guide describes what data to collect and procedures for completion of electronic case report form (eCRFs.) Completed eCRFs will be reviewed by clinical monitors on a regular basis throughout the trial by comparison against the source documents.

Study data will come from the eCRFs and other data sources including an electronic file containing plasma concentrations for naltrexone and 6b-naltrexole as well as the PK parameters. eCRFs for this study were created using an EDMS based on a Zelta by Merative Operating System. eCRFs were created using an established data dictionary for each variable including the field name, field type, field attributes, and coding for variables. Range checks, alpha-numeric requirements, and null/not null parameters were programmed as applicable. The back end database application is Oracle. Data entered into the EDMS system will be reviewed by Cognitive Research Corporation (CRC) clinical monitors and Fast-Track data managers. If incomplete or inaccurate data are found, the data will be queried in the system for site staff to address. The site will resolve data inconsistencies and errors using the EDMS with full audit trail of corrections being maintained within the system. Corrections and changes to the data will be reviewed by CRC clinical monitors and Fast-Track data managers.

Additional edit checks will be written to detect anomalies in the database. These checks will address inconsistencies (within visits, across visits), invalid/unusual values, missing values, and protocol violations. Edit checking will be validated on test data or actual clinical trial data. In addition to programmed edit checks, quality control examination of data will also be performed on reviews of data listings.

## **10. STATISTICAL CONSIDERATIONS**

### **10.1. General Considerations**

For descriptive purposes, dichotomous and categorical variables will be presented as number of observations and percentages; continuous variables will be given as means, standard deviations (SD), median, minimum (min) and maximum (max). All data will be presented in listings. Table, listing, and figure shells are presented in Section 13. Data will be summarized by each of the 2 Biopin 6 treatment groups and by placebo control group.

### **10.2. Participant Accountability and Protocol Deviations**

A summary will be prepared for the disposition of all consented subjects along with the reason(s) for early discontinuation. Reasons for not meeting the protocol eligibility criteria and protocol deviations will be presented as listings.

### **10.3. Demographics and Other Baseline Characteristics**

Summaries of the characteristics of the subjects in each of the study groups at baseline will be prepared for the safety analysis set. Demographic characteristics (e.g., age, gender, race, and ethnicity), height, weight, and body mass index will be summarized. Blood alcohol levels, birth control methods, and pregnancy test results will be presented in a listing. Screening naloxone challenge tests vital signs and pupil diameter will be summarized for each timepoint including change from the predose value. Other signs of a response to naloxone (sneezing/coughing, yawning, lacrimation, rhinorrhea, shivering, restlessness, sweating, vomiting, gooseflesh) will be summarized by sign, timepoint and severity score at each timepoint. All of these data will also be presented in a listing by subject. Other listings will include medical history terms and physical examination findings.

### **10.4. Drugs of Abuse**

The numbers and percentages of subjects with a positive urine drug test at each timepoint by treatment group will be presented.

### **10.5. Study Treatments**

The number and type of implant (Biopin 6 or placebo) will be presented by study group. A listing including this data as well as the distance of the incision to the closest palpable edge of each implant along with the date and time of the implant and if problems were encountered will also be provided.

Visual evaluation of the incision site and gross descriptions and microscopic descriptions of each implant at the time of implant explant will also be provided in a listing. Summaries of the severity grade for the visual inspections including wound infection, bleeding, and scarring, and the presence of absence of paresthesia, perforation, implant migration, implant extrusion, wound dehiscence, and implant fragmentation will also be summarized.

## **10.6. PK Analysis**

Concentration-time profiles will be presented graphically for each subject and by mean  $\pm$  standard error of the mean (SEM) by Biopin 6 group by nominal time point for naltrexone and 6b-naltrexole. The concentration-time profiles will be evaluated by non-compartmental analysis to determine PK parameters. Actual sample times will be utilized for calculations. Calculations of parameters will be performed with Phoenix WinNonLin 8.4 (Certara, Radnor, PA). The elimination rate constants ( $\lambda_z$ ) will be estimated from the terminal log-linear decline in plasma concentrations and  $t_{1/2}$  calculated as  $\ln(2)/\lambda_z$ . Area under the plasma concentration curves will be determined till the last time of a quantifiable plasma concentration ( $AUC_t$ ) by the log/linear trapezoidal rule and to infinity ( $AUC_\infty$ ) based on the last plasma concentration ( $C_t$ ) and  $\lambda_z$ . The value of  $t_{max}$  will be the observed time of the highest plasma concentration and  $C_{max}$  would be the plasma concentration at that time. Mean, SD, geometric mean, median, minimum and maximum will be presented for each PK parameter.

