**End of study: week 12 (resident, then non-resident)**

Subjects will return for a residential visit on week 12 after dosing. At that time, the implant will be removed and be subject to gross and microscopic descriptions and photos of each tissue capsule. Repeat assessment will be made of adverse effects, EKG, vital signs, clinical chemistry, hematology, concomitant medications, urine drugs, suicidality/depression. To verify diminution

of naltrexone exposure post-implant-removal, blood will be taken for PK pre-explant; 1, 3, 6, 12, 24 hrs after explant (as resident); and 48, 72, and 96 hours after explant (as non-resident).

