### 7.8.2 Pharmacokinetic considerations

Progression of dose levels (entrance of a new cohort at the next higher dose level) will also depend on review of the naltrexone PK data of the prior dose level. AUC (0-T) will be calculated for T=4 weeks, T= 8 weeks, and T=12 weeks for each subject, statistically summarized for the group, and the mean values will be compared to the reference values for the most sensitive animal species (dog) for which AUC was 3,267 ng/ml x hr up to 4 weeks, 6,117 ng/ml x hr up to

8 weeks, and 13.239 ng/ml x hr up to 12 weeks. In addition, the mean Cmax for dog for which the reference value was 42 ng/ml. If the mean clinical Biopin AUC or Cmax values exceed any of these reference values by 31%, the new cohort will not be entered until further consultation with the FDA.

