Blood sampling (29 samples)			Predose. Hours 1, 3, 6, 12, 24, 48 and 72. Days 7 and 10. Weeks 2, 3, 4, 5, 6, 7, 8, 9, 10, 11	Week 12: pre-explant and 1, 3, 6, 12, 24 hrs after explant (as resident). 48,72, and 96 hrs (non resident).

 Heart rate (sitting), blood pressure (sitting), respiratory rate, oral temperature

 ALT, albumin, alkaline phosphatase, AST, bilirubin (total and direct), calcium, chloride, cholesterol, creatinine, GGT, glucose, phosphate, potassium, sodium, total protein, uric acid, and blood urea nitrogen (BUN).

 Hemoglobin, hematocrit, red blood cell count (RBC), reticulocytes, white blood cell count (WBC), platelets

 Fibrinogen, prothrombin time (PT), and partial thromboplastin time (PTT).

 Subjects return for a non-residential visit on week 14 for surgical evaluation of explantation site

 For non-resident days, window will be target day [Week 2 (Day 14), Week 3 (Day 21), etc.] +/- 3 days

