## 5. STUDY ENDPOINTS

### 5.1. Pharmacokinetics

The following PK parameters will be determined for naltrexone and 6b-naltrexole:

**AUCt:** Area under the plasma concentration-time curve from time 0 to the time (t) of last quantifiable concentration (Ct) calculated by the log-linear trapezoidal rule.

**AUC∞:** Area under the plasma concentration-time curve from time 0 extrapolated to infinity. The terminal area from Ct to infinity was calculated by using the approximation as Ct/λz thus AUC∞ = AUCt + Ct/λz.

**Cmax:** The maximum observed plasma concentration.

**tmax:** The observed time to reach maximum plasma concentration.

**λz:** The terminal-phase exponential rate constant as calculated from the negative slope of the regression line for the terminal linear portion of the LN transformed plasma concentration versus time curve.

**t½:** The apparent terminal exponential half-life, calculated as ln(2)/λz.

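### Cmax and tmax are taken over all samples, including the eight drawn after explant, so a peak caused by removal, if one occurred, would be reported as the implant's own

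*SAP*

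**What the plan says.** SAP 5.1 defines Cmax as "The maximum observed plasma concentration" and tmax as the time at which it is reached. SAP 10.6 repeats the rule: tmax "will be the observed time of the highest plasma concentration and" Cmax is the concentration at that time. Protocol 9.1 uses the same definitions. Non-compartmental analysis is run on the concentration-time profile, with no split at removal.

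The SAP's Protocol Timetable lists "Blood sampling (29 samples" in total: "Predose. Hours 1, 3, 6, 12, 24, 48 and 72. Days 7 and 10", then "Weeks 2, 3, 4, 5, 6, 7, 8, 9, 10, 11", then nine samples at week 12. The protocol synopsis (End of study: week 12) describes the last group: "blood will be taken for PK pre-explant; 1, 3, 6, 12, 24 hrs after explant (as resident", followed by 48, 72 and 96 h as a non-resident. It says that they are taken to confirm that naltrexone exposure falls once the implant is out.

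SAP Table 11 has one Cmax row and one tmax row. It includes AUC rows limited in time (AUC0-4 and AUC0-8) but no in-situ version of Cmax or tmax. Nothing in either document limits these two parameters to the period when the implant is in place.

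**The concern.** The PK parameters are the primary objective, and Cmax and tmax are meant to describe how the implant releases drug. The post-explant samples answer a different question, namely whether exposure falls after removal. Under the rule as written, a concentration drawn 1 h after surgery competes on equal terms with the 20 post-dose samples drawn with the implant in place.

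If handling or cutting the implant released drug, the resulting peak would enter the primary summary as the product's Cmax, with a tmax just beyond week 12. Protocol 4.1 intends the product for six-monthly use, so a patient who keeps the implant would not meet that peak at week 12. Table 11 reports a mean and a geometric mean for tmax, so one such subject would shift both.

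The purpose given for the post-explant samples also has no summary statistic of its own, because no planned output relates post-explant to pre-explant levels within a subject.

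**Working it through.** **1. Sample count** (Protocol Timetable, both documents).

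- Predose to 72 h: 8
- Days 7 and 10: 2
- Weeks 2 to 11: 10
- Pre-explant at week 12: 1
- 1, 3, 6, 12, 24, 48, 72 and 96 h after explant: 8

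Total: 8 + 2 + 10 + 1 + 8 = 29, which reproduces the documents' figure. In place: 21, of which 20 are post-dose. After removal: 8, or 8/28 of the post-dose samples.

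**2. Times that tmax can take.** Week 12 is nominally 12 × 168 = 2,016 h. Restricted to in-situ samples, nominal tmax cannot exceed 2,016 h. As written, it can also be 2,017 to 2,112 h.

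**3. Effect of one affected subject on mean Cmax.** SAP section 8 gives six evaluable active subjects per level. Assume that all six have the same in-situ Cmax and that one has a post-explant peak k times that value. The values of k are assumptions, because the documents give none.

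- Arithmetic mean rises by (k − 1)/6.
- Geometric mean rises by k^(1/6) − 1.

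| k | Arithmetic mean | Geometric mean |
|---|---|---|
| 1.25 | +4.2% | +3.8% |
| 1.5 | +8.3% | +7.0% |
| 2 | +16.7% | +12.2% |
| 3 | +33.3% | +20.1% |

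**4. Effect on tmax.** Assume five subjects peak at 48 h and one at 2,017 h.

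- Mean: (5 × 48 + 2,017)/6 = 2,257/6 = 376 h, against 48 h without the affected subject's late peak.
- Geometric mean: 48 × (2,017/48)^(1/6) = about 89 h.
- Median: 48 h, unchanged.

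**5. No release at removal.** The case least favourable to the present rule is a flat in-situ profile, where assay and within-subject noise alone could put the maximum after explant. I simulated 200,000 subjects with an assumed residual CV of 10% to 30% and an assumed washout half-life of 4 to 24 h (the documents give neither).

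- Profile flat from the first sample: 0.1% to 7.8% of subjects have their maximum after explant, and mean Cmax rises by at most 0.9%.
- Profile rising over the first 24 h and then flat: 0.1% to 9.8%, and at most 1.2%.

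**6. What the documents say about profile shape.** Protocol 7.8.2 gives dog AUCs of 3,267 to 4 weeks, 6,117 to 8 weeks and 13.239 to 12 weeks. I read the last as 13,239. Each 4-week interval is 672 h, so the mean levels are:

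- Weeks 0 to 4: 3,267/672 = 4.9 ng/ml
- Weeks 4 to 8: (6,117 − 3,267)/672 = 4.2 ng/ml
- Weeks 8 to 12: (13,239 − 6,117)/672 = 10.6 ng/ml

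The dog Cmax is 42 ng/ml, with no time stated. These figures fit neither a flat plateau nor a profile dominated by an early peak. The in-situ shape in humans therefore cannot be fixed from the documents, and the share of subjects whose maximum would fall after explant cannot be estimated.

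**The case against.** The strongest case for leaving the rule alone has four parts.

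**No removal peak is documented.** The protocol expects exposure to fall. A reader might infer that release at removal is foreseen, because SAP 10.5 plans to record "implant migration, implant extrusion, wound dehiscence, and implant fragmentation" at explant. The documents do not support that. Fragmentation is one entry in an inspection list and is nowhere linked to plasma levels. This part stands: the point is conditional.

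**A large distortion needs strong assumptions.** A reader might infer that most subjects would have their maximum after explant. That would require a flat in-situ plateau and a raised level after removal in every subject. Step 6 gives no support for the first, and nothing in the documents supports the second. Nor do the dog figures support the opposite assumption, an early in-situ peak high enough to make a removal peak irrelevant.

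**Dose progression is hardly affected.** Protocol 7.8.2 compares mean Cmax with the dog value, "for which the reference value was 42 ng/ml", so a reader might infer that escalation decisions are at risk. SAP section 3 says that the third level was not entered and that the SAP was finalised after dose-level 2 data were available, so an SAP change cannot alter escalation. An inflated Cmax would in any case have acted cautiously, by prompting consultation with the FDA.

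**The peak would not be hidden.** SAP Tables 9 and 10 give each post-explant time its own row, Figure 5 plots individual profiles, and Table 11 shows the tmax median and range. This stands for a careful reader. The headline Cmax and tmax would still mix two processes, and for a subject explanted early the 2,016 h mark would not identify the peak.

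**Conclusion.** The point holds as a conditional weakness in how two primary parameters are defined. By their stated rule, the SAP and Protocol 9.1 admit eight post-explant samples to Cmax and tmax, although those samples serve another purpose. That all samples count follows from the absence of any window; neither document says so in terms.

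If removal releases drug in one of six subjects, to 1.5 to 2 times the in-situ Cmax, mean Cmax rises by 8% to 17%, assuming equal in-situ Cmax. Mean tmax can move from 48 h to 376 h in the example given. If removal releases nothing, mean Cmax changes by about 1% or less under the assumptions in step 5. The documents do not settle which case applies. The finding does not extend to dose escalation, or to a claim that a removal peak is expected.

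**What to change.** In SAP 5.1, 10.6 and Table 11:

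- Add in-situ Cmax and tmax, derived from predose through the pre-explant sample, or up to the actual explant time if the implant comes out earlier. Use these to describe release from the implant.
- Keep the all-sample Cmax and tmax beside them, so that the SAP does not depart from Protocol 9.1 on a primary parameter.
- Add the highest post-explant concentration and its ratio to the pre-explant value. The ratio directly answers the question for which those samples were taken.
- Record the addition in SAP section 3 as made after dose-level 2 data were available.

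The cost is some SAP wording, a few table rows and a post-data addition to disclose. No new data are needed. If there was no removal peak, the two versions of Cmax will nearly agree. If there was one, the in-situ values remain interpretable and the peak appears in its own row.

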## **10.7. Safety Analysis**

### **10.7.1. Adverse Events**

AEs will be coded using the most recent version of the Medical Dictionary for Regulatory Activities (MedDRA) and will be grouped by system, organ, and class (SOC) and preferred term (PT) designation. The severity, frequency, and relationship of AEs to investigational product will be presented by SOC and PT groupings. Listings of each individual AE including start date, stop date, severity, relationship to IP, outcome, action taken (including any treatment administered), and duration will be provided.

Every AE will be assessed for whether or not it qualifies as an SAE. All SAEs will be categorized and listed according to the following categories: Congenital Anomaly or Birth Defect; Persistent or Significant Disability/Incapacity; Results in Death; Requires or Prolongs Hospitalization; Other Medically Important Serious Event; or Life-Threatening. For deaths, the date and cause of death will be collected and listed. For hospitalizations, the dates of admission and release (discharge) will be collected and listed.

Each AE (based on PT) will be counted once only for a given study subject. If the same AE occurred on multiple occasions, the highest severity will be assumed. Thus, study subjects are not counted multiple times in a given numerator in the calculation of frequencies for a specific AE. C-SSRS reports of suicidality or suicidal ideation will be reported as AEs and analyzed as AEs if the investigator determines after an interview with the subject, that the responses are consistent with suicidal ideation or attempt.

### **10.7.2. Implant Visual Inspection**

The incision site will be examined at each visit post implant. At each timepoint for each group, the severity grades for wound infection, bleeding, and scarring, and the presence or absence of paresthesia, perforation, implant migration, implant extrusion, and wound dehiscence will also be summarized.

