#### Secondary:

Adverse events (AEs), clinical laboratory values.

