#### **4.1.2. Secondary**

Secondary objectives include determining the safety of BIOPIN 6 implants by assessing adverse events, incision/implant site local reactions, clinical laboratory data, and vital signs.

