### **10.7.3. Suicidality and Depression**

The number and percentage of subjects that endorse suicidal ideation and suicide attempt at any time during the study will be presented based on the responses to the Columbia Suicide Severity Rating Scale (CSSR-S). For HAM-D17 scores, the mean, SD, change from Day -1, median, and range of all values at each time point will be presented in a summary table. The number and percentages of subjects with scores greater than 7, that is considered to be indicative of clinical depression will be presented for all timepoints.

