### **9.7.4 Clinical Laboratory**

Descriptive statistics will be generated for all tests performed at screening and at each clinic visit. If a laboratory analysis is repeated, the last measurement performed prior to the clinic visit will be used in the summary statistics for that clinic visit. If an unscheduled clinical laboratory visit occurs prior to a scheduled visit that is missed due to dropout, then the unscheduled visit will be used in the summary statistics for the missed scheduled clinical visit. If an unscheduled clinical laboratory visit occurs between two scheduled clinical visits, then the data from the unscheduled visit will only be presented in the listings and not in summary statistics. In addition, at each post-randomization clinic visit descriptive statistics for change from baseline will be generated for clinical chemistry and hematology tests. Laboratory values will be plotted as mean  $\pm$  standard error over time. All laboratory measurements will be presented in the listings including an assessment if the laboratory value is considered within normal limits or is not clinically significant or is clinically significant.

The number and percentage of positive urine drug tests and pregnancy tests for screening visits and all treatment and follow-up visits will be tabulated. Results of all urine drug tests and pregnancy tests will be presented in the listings. The percentage of subjects with a positive urine drug test at any time post start of treatment will also be presented by test type and treatment group.

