**Table 8: Study Treatment –Explants Inspection at Time of Explant**

	Biopin 6 1 implant	Biopin 6 2 implants	Placebo 1 to 2 implants
Assessment	(N=xx)	(N=xx)	(N=xx)
Duration of Implant period (days)			
Mean (SD)	xx (xx.x)	xx (xx.x)	xx (xx.x)
Min - Max	xx - xx	xx - xx	xx - xx
Wound Infection			
N	xx	xx	xx
None, n (%)	xx (xx.x)	xx (xx.x)	xx (xx.x)
Mild, n (%)	xx (xx.x)	xx (xx.x)	xx (xx.x)
Moderate, n (%)	xx (xx.x)	xx (xx.x)	xx (xx.x)
Severe, n (%)	xx (xx.x)	xx (xx.x)	xx (xx.x)
Bleeding			
N	xx	xx	xx
None, n (%)	xx (xx.x)	xx (xx.x)	xx (xx.x)
Mild, n (%)	xx (xx.x)	xx (xx.x)	xx (xx.x)

	Biopin 6 1 implant	Biopin 6 2 implants	Placebo 1 to 2 implants
Assessment	(N=xx)	(N=xx)	(N=xx)
Duration of Implant period (days)			
Mean (SD)	xx (xx.x)	xx (xx.x)	xx (xx.x)
Min - Max	xx - xx	xx - xx	xx - xx
Moderate, n (%)	xx (xx.x)	xx (xx.x)	xx (xx.x)
Severe, n (%)	xx (xx.x)	xx (xx.x)	xx (xx.x)
Scarring			
N	xx	xx	xx
None, n (%)	xx (xx.x)	xx (xx.x)	xx (xx.x)
Mild, n (%)	xx (xx.x)	xx (xx.x)	xx (xx.x)
Moderate, n (%)	xx (xx.x)	xx (xx.x)	xx (xx.x)
Severe, n (%)	xx (xx.x)	xx (xx.x)	xx (xx.x)
Paresthesia			
N	xx	xx	xx
None, n (%)	xx (xx.x)	xx (xx.x)	xx (xx.x)
Perforation			
N	xx	xx	xx
None, n (%)	xx (xx.x)	xx (xx.x)	xx (xx.x)
Implant Migration			
N	xx	xx	xx
None, n (%)	xx (xx.x)	xx (xx.x)	xx (xx.x)
Implant Extrusion			
N	xx	xx	xx
None, n (%)	xx (xx.x)	xx (xx.x)	xx (xx.x)
Wound Dehiscence			
N	xx	xx	xx
None, n (%)	xx (xx.x)	xx (xx.x)	xx (xx.x)
Implant Fragmentation			
N	xx	xx	xx
None, n (%)	xx (xx.x)	xx (xx.x)	xx (xx.x)

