**Table 21: Incision Site Visual Inspection**

	Biopin 6 1 implant	Biopin 6 2 implants	Placebo 1 to 3 implants
Assessment	(N=xx)	(N=xx)	(N=xx)
Repeat for each visit: Day 1, 2, 3, 4, 7, 10, Weeks 2, 3, 4, 5, 6, 7, 8, 9, 10, 11, 12			
Wound Infection			
N	xx	xx	xx
None, n (%)	xx (xx.x)	xx (xx.x)	xx (xx.x)
Mild, n (%)	xx (xx.x)	xx (xx.x)	xx (xx.x)
Moderate, n (%)	xx (xx.x)	xx (xx.x)	xx (xx.x)
Severe, n (%)	xx (xx.x)	xx (xx.x)	xx (xx.x)
Bleeding			
N	xx	xx	xx
None, n (%)	xx (xx.x)	xx (xx.x)	xx (xx.x)
Mild, n (%)	xx (xx.x)	xx (xx.x)	xx (xx.x)
Moderate, n (%)	xx (xx.x)	xx (xx.x)	xx (xx.x)
Severe, n (%)	xx (xx.x)	xx (xx.x)	xx (xx.x)
Scarring			
N	xx	xx	xx
None, n (%)	xx (xx.x)	xx (xx.x)	xx (xx.x)
Mild, n (%)	xx (xx.x)	xx (xx.x)	xx (xx.x)
Moderate, n (%)	xx (xx.x)	xx (xx.x)	xx (xx.x)
Severe, n (%)	xx (xx.x)	xx (xx.x)	xx (xx.x)
Paresthesia			
N	xx	xx	xx
None, n (%)	xx (xx.x)	xx (xx.x)	xx (xx.x)
Perforation			
N	xx	xx	xx
None, n (%)	xx (xx.x)	xx (xx.x)	xx (xx.x)
Implant Migration			
N	xx	xx	xx
None, n (%)	xx (xx.x)	xx (xx.x)	xx (xx.x)
Implant Extrusion			
N	xx	xx	xx
None, n (%)	xx (xx.x)	xx (xx.x)	xx (xx.x)
Wound Dehiscence			
N	xx	xx	xx
None, n (%)	xx (xx.x)	xx (xx.x)	xx (xx.x)

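### Site-inspection findings are tabulated only by scheduled visit, so Table 21 does not generally show how many subjects were ever affected, or their worst grade, once a sign is seen at two or more visits

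*SAP*

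**What the plan says.** SAP 4.1.2 makes site reactions part of the secondary safety objective, to be met by "assessing adverse events, incision/implant site local reactions, clinical laboratory data, and vital signs". The protocol synopsis (section 2.1) is narrower and names only "Adverse events (AEs), clinical laboratory values".

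SAP 10.7.2 sets the summary: "At each timepoint for each group, the severity grades for wound infection, bleeding, and scarring, and the presence or absence of paresthesia", followed by perforation, migration, extrusion and dehiscence. That makes three graded signs and five yes/no signs. The Table 21 shell instructs: "Repeat for each visit: Day 1, 2, 3, 4, 7, 10, Weeks 2, 3, 4, 5, 6, 7, 8, 9, 10, 11, 12". It has no row across visits. Table 8, "Study Treatment –Explants Inspection at Time of Explant", adds one more single timepoint.

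For two other assessments the SAP text does plan a cumulative count. In 10.7.3 it covers subjects endorsing "suicidal ideation and suicide attempt at any time during the study will be presented". In the section printed as 9.7.4 it says: "The percentage of subjects with a positive urine drug test at any time post start of treatment will also be presented". For AEs, 10.7.1 counts each preferred term once per subject at the highest severity. No such rule is given for the site inspection.

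**The concern.** The count at a visit is a point prevalence. A reader asking about local tolerability of one disc, two discs and placebo mostly wants two other figures: how many subjects ever had the sign, and how bad it became. Neither can generally be recovered from counts at separate visits, because the table does not link subjects from one visit to the next.

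There is also a coverage gap. Protocol 8.3 has the implant parameters assessed at every visit and also whenever the subject raises a problem. Table 21 lists scheduled visits only. A finding that prompts an extra inspection and clears before the next visit has no row in it.

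At stake is how completely one named part of the SAP's secondary objective is summarised. Data collection, sample size and error rates are not affected.

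**Working it through.** The plan states no figure on this point, so there is nothing to reproduce. The check asks what Table 21 can and cannot determine.

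**Inputs**
- Visits (Table 21): Days 1, 2, 3, 4, 7 and 10 are 6; Weeks 2 to 12 are 11; 6 + 11 = 17.
- Group sizes (SAP 4.2 and 10.1): 6 active and 2 placebo per cohort, two cohorts, placebo pooled. This gives 6 on one disc, 6 on two discs and 2 × 2 = 4 on placebo, 16 in all if enrolled as planned.
- Assumption: every subject in the group is inspected at every visit, so N is constant.

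**Formula.** If c_1, ..., c_k are the numbers positive at the visits where the sign was seen, the number ever affected at scheduled visits lies between max(c_i) and min(N, sum of c_i). The lower bound applies when the positives overlap as much as possible. The upper bound applies when they overlap as little as possible.

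**Results with one positive subject at each of k visits**

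| N | k | Lower | Upper |
|---|---|---|---|
| 6 | 1 | 1/6 (16.7%) | 1/6 (16.7%) |
| 6 | 2 | 1/6 (16.7%) | 2/6 (33.3%) |
| 6 | 3 | 1/6 (16.7%) | 3/6 (50.0%) |
| 6 | 6 or more | 1/6 (16.7%) | 6/6 (100%) |
| 4 | 1 | 1/4 (25%) | 1/4 (25%) |
| 4 | 2 | 1/4 (25%) | 2/4 (50%) |
| 4 | 4 or more | 1/4 (25%) | 4/4 (100%) |

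The count is exact when the bounds meet: no finding at any visit, a finding at one visit only, or all N positive at some visit. Even then it covers scheduled inspections only.

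**Worst grade.** Suppose scarring is mild in one subject at one visit and moderate in one subject at the next. This fits one subject who worsened (worst grade: one moderate). It equally fits two subjects (worst grade: one mild, one moderate). The table prints the same rows for both.

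**Could another planned table supply the figure?**
- Table 8 covers the explant inspection only.
- Tables 13 and 18 count subjects once per preferred term, and Table 18 shows maximum severity. Both are restricted to recorded AEs.
- Protocol 10.6 says how laboratory and vital-sign abnormalities are considered as AEs. No visible text does the same for inspection findings.

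**The case against.** The strongest reply is that the clinically important cases are already covered. Protocol 10.1 defines an AE as any untoward medical occurrence, related or not, and Protocol 4.4 lists infection, extrusion, bleeding and dehiscence as risks of the procedure. A clinically evident infection or extrusion should therefore be recorded as an AE. Tables 13 and 18 would then separate one infected subject from three. This stands, and it limits the point to findings not recorded as AEs and to off-schedule inspections.

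Other parts of the reply also stand:
- SAP 10.1 lists all data. With 16 planned subjects the counts can be made by hand.
- The study is descriptive (SAP 7), and the safety progression rules in Protocol 7.8.1 use adverse reactions. SAP 3 records that escalation ended after dose level 2. No decision depends on Table 21.
- Site reactions are named in the SAP's secondary objective but not in the protocol synopsis.
- The comparators are text only: the shells for Tables 22 and 28 are themselves by visit.
- A worst-ever grade mixes implant-day bleeding with later bleeding, and some scarring is to be expected after an incision. Timing matters for these signs, so the by-visit rows are worth keeping.

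The reply does not remove the point. A count made by hand from listings has no stated rule for worst grade, denominator or unscheduled inspections. Protocol Appendix A and the listing shells are redacted, so a rule there that turns inspection findings into AEs cannot be excluded. Such a rule would narrow the gap, but it would not change Table 21.

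**Conclusion.** The point holds as a gap in the summary. When a sign is seen at two or more visits, Table 21 generally leaves the number ever affected and the worst grade undetermined. For N = 6 and one positive subject at each of three visits, the range is 1/6 to 3/6. The ambiguity matters for findings that may not be recorded as AEs, such as mild scarring, paresthesia or migration. Off-schedule inspections have no row.

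A reader might infer that the number of subjects with an infection or extrusion will be unavailable, or that the groups cannot be compared on local tolerability at all. The documents do not support either inference: the AE tables should carry such events once per subject, and the listings hold everything else.

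The conclusion assumes groups of 6, 6 and 4 as planned, full attendance at inspections, and no redacted rule that makes every inspection finding an AE. It is a low-priority, inexpensive improvement and not an error in the results.

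**What to change.** Add a first block to Table 21, by group, for any post-implant inspection, unscheduled inspections included:
- Wound infection, bleeding and scarring: each subject counted once at worst grade (none, mild, moderate, severe).
- Paresthesia, perforation, migration, extrusion and dehiscence: n (%) of subjects in whom the sign was ever present.
- Denominator: subjects in the Safety Analysis Set with at least one post-implant inspection.

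Put the same rule in SAP 10.7.2 and keep the by-visit rows below the block. Because the SAP was finalised after dose-level 2 data were available, record the addition as a change in the clinical study report, as Protocol 9.5.3 provides.

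Two small shell points can be settled in the same edit. The yes/no signs currently show only a row for none, so presence has to be inferred by subtraction. Table 21 also stops at Week 12, although a Week 14 evaluation of the explantation site is scheduled, so the SAP should say whether that visit counts.

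The cost is one extra table block and a sentence of SAP text. No new data are needed, and neither sample size nor any error rate changes.
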